### 3.3.3. Risk-benefit Assessment

In the non-clinical setting, Debio 1347 exhibits high anti-tumour activity both in vitro and in vivo in cancers with amplification, mutation or translocation/fusion of the FGFR1, 2 or 3 genes, and cancers with overexpression of FGFR(s). This compound is regarded as an innovative therapeutic opportunity for cancer patients with genetic alterations in the FGFR1-3 genes or overexpression of the FGFR1-3 proteins.

In non-clinical safety studies of Debio 1347 in rats and monkeys, the principal target organs of toxicity were bone/cartilage, epithelial tissues and the kidneys. In addition, effects on lymphohaematopoietic tissues, liver and the gastrointestinal tract were observed. Mineralisation in multiple organs was also seen (such as trachea, stomach, kidneys, eyes in rats), with a broader range of organs and tissues affected in rats than in monkeys. On the other hand, periosteal changes occurred only in monkeys but not in rats. Except for thoracic deformity and mineralisation in multiple organs in rats, the changes seen in rats and monkeys in the 4-week repeated-dose toxicity studies either reversed or tended to reverse over the 4 week recovery period.

As a result, soft-tissue mineralisation, bone/cartilage effects, lymphohaematopoietic abnormalities, gastrointestinal and hepatic disorders, and ophthalmological disorders (mainly corneal mineralisation) are under close monitoring in the clinical setting. Subjects with phosphate/calcium homeostasis impairment are contraindicated. In addition, subjects with osteoporosis should be closely monitored. Investigators should reassess the risk-benefit ratio for each of their subjects.

Debio 1347 may have an in vivo phototoxic risk based on an in vitro phototoxicity test using a fibroblast cell line, where the compound was suggested as a phototoxic substance; and a whole-body autoradiography in rats after single oral dose of 1 mg/kg of [ $^{14}$ C] Debio 1347 suggesting a slower elimination rate of Debio

1347 from skin compared with blood. On the basis on these findings, subjects should avoid excessive exposure to sun/UV light.

Although reproductive and developmental toxicity studies of Debio 1347 have not been conducted, some changes in the reproductive organs, such as thinning of vaginal mucosal epithelium and atrophic changes in testes, epididymides, the prostate gland, seminal vesicles and the uterus were observed at the lethal dose in preliminary dose-repeated toxicity studies in rats. From these findings and those reported above on bone and cartilage, it is inferred that Debio 1347 may affect reproduction and development; pregnancy/breastfeeding are therefore strictly contraindicated.

In safety pharmacology studies, no effects on the central nervous system or respiratory system were seen in rats at Debio 1347 doses up to 100 mg/kg. Debio 1347 was a potent hERG inhibitor in vitro, but the compound did not modify blood pressure, heart rate, and ECG or body temperature at doses up to 10 mg/kg in the monkey telemetry study. Although Debio 1347 potential for affecting cardiac function is considered to be low based on the study in monkeys, this potential risk is under close monitoring in the ongoing Phase I trial.

Based on current knowledge, Debio 1347 is deemed to have a limited risk of being victim of PK interaction from other drugs. In contrast, as per in vitro results available so far, Debio 1347 is considered at possible risk for perpetrating DDIs towards sensitive substrates of CYP1A2, CYP3A, P-gp, BCRP, MATE1 and OCT2 through inhibition and/or induction of drug metabolism or transport. In addition, BSEP may be inhibited as well.

The clinical impact of these in vitro observations is not known. Subjects who are taking concurrent drugs that are known substrates of either CYP3A, CYP1A2, P-gp, BCRP, MATE1 or OCT2 should be carefully monitored. In addition, potential changes in bile salts plasma concentration should be monitored during treatment with Debio 1347.

Carcinogenicity studies or local tolerance studies have not been conducted to date.

No trend towards QTc prolongation was evident from the local ECG measurements collected during the study. An additional exposure-response analysis based on ECG central reading was not fully conclusive regarding the QTcF prolonging potential of Debio 1347, but indicate that the potential increase (predicted upper bound of the 90% CI for  $\Delta$ QTcF was 11.44 and 12.55 milliseconds at the recommended dose of 80 and the highest dose of 150 mg, respectively) would remain below the 20 milliseconds threshold usually considered for oncology products. Furthermore, there were no relevant changes for the other ECG intervals of interest (QRS, RR, PR) after Debio 1347 and no relevant changes were evident from the categorical analysis or from the analysis of morphological abnormalities.

To mitigate the inherent risks in the current clinical study of Debio 1347, subjects are closely monitored while they are receiving treatment.

Debio 1347 seems to be generally well tolerated and the observed toxicity profile to date has been consistent with the expected effect of a selective and potent inhibitor of the FGFR pathway, the benefit/risk profile is assessed as positive. Further clinical research with Debio 1347 is therefore warranted.

## 4. OBJECTIVES

### 4.1. Objectives

#### 4.1.1. Primary objective

To assess the efficacy of Debio 1347 in terms of objective response rate (ORR) in subjects with solid tumors harboring FGFR1-3 gene fusion/rearrangement.

#### 4.1.2. Secondary objectives

1. To evaluate the efficacy of Debio 1347 in terms of duration of response (DoR), DCR, progression free survival (PFS) and overall survival (OS).
2. To assess the safety of Debio 1347.
3. To assess exposure-response relationships vs efficacy and safety (notably QTcF).

[figure not shown]
[REDACTED]

## 5. STUDY DESIGN AND TREATMENT

### 5.1. Study Design

This is a multicentre, basket, two stage, adaptive single arm Phase II study to examine the efficacy of Debio 1347 administered at the recommended Phase II dose of 80 mg in subjects with solid tumors harboring FGFR1-3 gene fusion/rearrangement. The study will include 3 cohorts of subjects comprising biliary tract cancer (Cohort 1), urothelial cancer (Cohort 2) and, in Cohort 3, all other solid tumor histologies not included in Cohorts 1-2, such as non small cell lung cancer (NSCLC), head and neck cancer, thyroid cancer, oral cancer, breast cancer, prostate cancer and others but excluding primary brain tumors.

Stage 1 will require 27 evaluable subjects across the three cohorts assuming an equal accrual rate per cohort. Stage 2 will require 86 evaluable subjects across all cohorts or per individual cohort depending on results of assessments scheduled at the end of Stage 1 (see graphical algorithm below and Section 11). Assuming a drop out rate of 10%, up to 125 subjects will be enrolled into the study.

Subjects will be treated with Debio 1347 daily in 28-day cycles until the occurrence of disease progression (clinical or radiologic) or unacceptable toxicity (other treatment discontinuation criteria are described in Section 8.4.1). Subject safety (AEs) and survival will be followed-up respectively for 30 days after the last Debio 1347 dose and every 12 weeks from treatment end until death or loss to follow-up but no longer than for a total of 2 years after the last subject has discontinued treatment. Disease status will be followed-up every 12 weeks only in subjects without PD from treatment end until PD, death or loss to follow-up but no longer than for a total of 2 years after the last subject has discontinued treatment.

## 5.2. Study Treatment

Subjects will receive Debio 1347 tablets at the dose of 80 mg once daily from Day 1 to Day 28 in 28-day cycles until occurrence of any of the criteria described in Section 8.4.1.

Debio 1347 method of administration is described in Section 7.6.

## 5.3. Dose Modifications

### 5.3.1. Debio 1347 dose adjustment

Individual dose adjustment of Debio 1347 may be considered and applied as per Table 5-1 below if required. Non-treatment related or unexpected toxicities may also require treatment interruption at the discretion of the Investigator and Medical Monitor. For guidance on toxicity management, please refer to appendices E, F, and G.

**Table 5-1 Debio 1347 dose adjustment**

ADVERSE EVENT	GRADE	ACTION
Febrile neutropenia, Neutropenia with infection	4	Permanent discontinuation
	3	Temporary discontinuation until recovery to ≤ Grade 1
Neutropenia	3, 4	Temporary discontinuation until recovery to ≤ Grade 2
Thrombocytopenia	4	Temporary discontinuation until recovery to ≤ Grade 1
	3	If a platelet transfusion is required, temporary discontinuation until recovery to ≤ Grade 1
Diarrhea, constipation, nausea, vomiting, alopecia or skin toxicity	3, 4	Temporary discontinuation until recovery to ≤ Grade 1, but Grade 2 diarrhea manageable with drugs can restart the treatment at 60 mg QD
Hypertension	4	Permanent discontinuation
	3	If uncontrolled, temporary discontinuation until recovery to ≤ Grade 2
Hepatotoxicity (e.g., AST, ALT, ALP increased)	4	Permanent discontinuation
	3	Temporary discontinuation until recovery to ≤ Grade 2
Other non-hematological toxicity (except for alopecia and clinically insignificant electrolyte abnormalities)	4	Permanent discontinuation
	3	Temporary discontinuation until recovery to ≤ Grade 1 or baseline
Hyperphosphatemia		Please refer to treatment guidelines in Appendix E
Recovery from the above AEs		Permanent discontinuation if failure to recover within 21 days, otherwise retreatment at 60 mg QD
Dermatologic toxicities		Please refer to treatment guidelines in Appendix F
Hypercalcemia		Please refer to treatment guidelines in Appendix G

Abbreviations: ALP, alkaline phosphatase; ALT, alanine aminotransferase; AST, aspartate aminotransferase; QD, once daily

In the event a subject requires temporary treatment discontinuation, the Investigator may choose to increase the frequency of the assessments until resolution.

Subjects will be permanently discontinued if a second reduction is necessary. Reduced doses may not be re-escalated. Nevertheless, if according to the Investigator a further increase of the dose to 80 mg daily is expected to improve the clinical benefit of a subject, this increase may be considered after discussion between the Investigator and the Medical Monitor of the study.

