### A. Initial Treatment

Serum phosphorus levels	Intervention
5.5 – 6.9 mg/dL	
Continue treatment with Debio 1347 at current dose AND start on sevelamer oral POWDER 1200mg three times a day (subjects may use tablets if preferred, but tends to have more gastrointestinal toxicity) AND
 
Escalate to sevelamer oral POWDER or tablets 2400mg three times a day if tolerated.
 <hr/> 
Reassess serum phosphorus within 7 days

≥ 7 mg/dL	
Hold treatment with Debio1347
 
Start sevelamer oral POWDER or tablets 2400mg three times a day
 <hr/> 
Add treatment with lanthanum carbonate (Fosrenol®) 1g three times a day
 <hr/> 
Reassess serum phosphorus level within 7 days: If serum phosphorus level < 5.5 mg/dL → resume Debio 1347 at same dose and recheck within 7 days of resumption

	
N.B.
 
 
- Sevelamer should be preferably taken in the mid of meals
 
- Lanthanum carbonate should be taken just after meals
 
- Sevelamer and lanthanum must be administered at least 2 hours after or 4 hours before Debio 1347
 

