## B. Second Modification on Treatment

Serum phosphorus level	Intervention
5.5 – 6.5 mg/dL	
Continue treatment with Debio 1347 at a current dose AND Continue sevelamer oral POWDER or tablets 2400mg three times a day
 <hr/> 
Introduce treatment with lanthanum carbonate (Fosrenol®) to 1.0g three times a day or increase to 1.5g three times a day
 <hr/> 
Reassess serum phosphorus level within 7 days

6.6-6.9 mg/dL	
Continue treatment with Debio 1347 at current dose AND Continue sevelamer oral POWDER or tablets 2400mg three times a day
 <hr/> 
Introduce treatment with lanthanum carbonate (Fosrenol®) to 1.0g three times a day or increase the dose to 1.5g three times a day
 <hr/> 
Add treatment with oral acetazolamide 250mg twice a day
 <hr/> 
Reassess serum phosphorus level within 7 days

≥ 7 mg/dL	
Hold treatment with Debio 1347 – consider dose reduction Continue sevelamer oral POWDER or tablets 2400mg three times a day
 <hr/> 
Increase treatment with lanthanum carbonate (Fosrenol®) to 1.5g three times a day AND
 <hr/> 
Add treatment with oral acetazolamide 250mg twice a day
 <hr/> 
Reassess serum phosphorus level within 7 days:
 
 
- If serum phosphorus level < 5.5 mg/dL → resume Debio 1347 with dose reduction
 

	
N.B.
 
 
- Sevelamer should be preferably taken in the mid of meals
 
- Lanthanum carbonate should be taken just after meals
 
- Sevelamer and lanthanum must be administered at least 2 hours after or 4 hours before Debio 1347
 
- Acetazolamide should be preferably taken just after breakfast and dinner
 

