### C. Subsequent Modifications

Serum phosphorus level	Intervention
> 5.5 mg/dL - 6.9mg/dL	
 
• If not already done, maximize regimen to include:               
 
- Sevelamer oral POWDER or tablets to 2400mg three times a day
 
- Lanthanum carbonate (Fosrenol®) to 1.5g three times a day
 
- Oral acetazolamide 250mg twice a day
 
 
 
• If regimen already maximized, consider dose reduction (without interrupting Debio 1347 assumption)
 
 <hr/> Reassess serum phosphorus level within 7 days
≥ 7 mg/dL	<hr/> Hold treatment with Debio1347 – dose reduction needed <hr/> Maximize regimen to include: 
 
- Sevelamer oral POWDER or tablets to 2400mg three times a day
 
- Lanthanum carbonate (Fosrenol®) to 1.5g three times a day
 
- Oral acetazolamide 250mg twice a day
 
 <hr/> Reassess serum phosphorus level within 7 days: 
 
- If serum phosphorus level < 5.5 mg/dL → resume Debio 1347 with dose reduction
 

	N.B. 
 
- Sevelamer should be preferably taken in the mid of meals
 
- Lanthanum carbonate should be taken just after meals
 
- Sevelamer and lanthanum must be administered at least 2 hours after or 4 hours before Debio 1347
 
- Acetazolamide should be preferably taken just after breakfast and dinner
 

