10.3.1 Extent of Exposure

Extent of exposure and compliance derived from the subject diary eCRF and "Date of last study drug intake" in the End Of Treatment CRF form will be summarized as continuous for the following:

- Date of last dose of study drug, defined as the "Date of last study drug intake" in the End Of Treatment CRF form, or if missing will be replaced with the date of last non-zero drug intake in the subject diary.
- Treatment duration (weeks), defined as (date of last dose of study drug – date of first dose + 1)/7.
- Number of completed 28-day cycles, defined as the integer value of floor(treatment duration in days/28). (Note: Report only the median, quartiles, min and max.)
- Cumulative dose (mg), defined as (total number of tablets taken during the study)*20 mg. Note: In the case of incomplete diary data over the treatment duration of the subject, the days

with missing tablet counts will be assumed to have a zero tablet count in the calculation of cumulative dose over the treatment duration.

- Planned cumulative dose (mg), defined as (treatment duration in days)*80 mg. For any period where there is a dose reduction this will be multiplied by 60 mg. Note: This quantity is not summarized, but only used in calculation of treatment compliance.

- Dose intensity (mg/day), defined as

$$\text{Cumulative dose (mg)} / \text{Treatment duration (days)}$$

- Treatment compliance (a.k.a. relative dose intensity) (%), defined as

$$(\text{Cumulative dose (mg)} / \text{Planned cumulative dose (mg)}) * 100$$

- Treatment compliance for first 4 cycles (%), defined as

$$(\text{Cumulative dose (mg) for the period where dose date} - \text{treatment start date} \leq 112 / \text{planned cumulative dose for first 4 cycles (112 multiplied by 80 mg. For any period where there is a dose reduction this will be multiplied by 60 mg.)})$$

Number (%) of patients will be presented for:

- Treatment compliance (≥ 75 , $< 75\%$)
- Treatment compliance for first 4 cycles (≥ 75 , $< 75\%$)
- Number of dose reductions: 0 or 1 dose reduction. (Note: Patients will be permanently discontinued if a second reduction is necessary and thus having > 1 dose reduction should not occur according to protocol procedures. If the > 1 dose reduction category occurs it will additionally be displayed).

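### Section 5.3.1 discontinues a subject who needs a second dose reduction, but Appendix E can call for a further reduction and resumption in a subject already reduced, and no text says which governs

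*Protocol*

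**What the plan says.** The starting dose is fixed in Protocol Section 5.2: "Subjects will receive Debio 1347 tablets at the dose of 80 mg once daily from Day 1 to Day 28". Section 5.3.1 governs adjustment through Table 5-1. For listed events that resolve, the recovery row requires permanent discontinuation if recovery takes more than 21 "days, otherwise retreatment at 60 mg QD". Below the table comes the limit: "Subjects will be permanently discontinued if a second reduction is necessary". The same paragraph rules out re-escalation, then allows a return to 80 mg after discussion with the Medical Monitor.

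For hyperphosphatemia, Table 5-1 gives no action of its own: "Please refer to treatment guidelines in Appendix E". Appendix E works in successive parts:

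- Part A (initial treatment): at 7 mg/dL or more, hold, then "resume Debio 1347 at same dose and recheck within 7 days of resumption" once phosphorus is below 5.5 mg/dL.
- Part B (second modification): at 7 mg/dL or more, hold, then "resume Debio 1347 with dose reduction" once below 5.5 mg/dL.
- Part C (subsequent modifications): at 7 mg/dL or more, hold, with "dose reduction needed", then resume at a reduced dose. Above 5.5 and up to 6.9 mg/dL on an already maximized phosphate-lowering regimen, a reduction without interruption is to be considered.

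SAP 10.3.1 restates the one-reduction limit, expects no subject to exceed it, and will display a category of more than one reduction if it occurs. For planned cumulative dose it says: "For any period where there is a dose reduction this will be multiplied by 60 mg".

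**The concern.** A subject reduced at part B whose phosphorus again reaches 7 mg/dL meets two instructions. Section 5.3.1 takes the subject off drug; part C of Appendix E holds, reduces and resumes. Part C is written without reference to the Section 5.3.1 limit, and no passage ranks the two.

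The sequence is foreseeable. Protocol Section 3.3.2 lists hyperphosphatemia among the most common adverse events in the Phase I study and among those most often above Grade 2. SAP 10.3.7 plans a count of subjects who received sevelamer, lanthanum carbonate and acetazolamide, and acetazolamide enters Appendix E only in parts B and C.

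Two things are at stake. Whether such a subject stays on treatment would depend on which text the site applied. The exposure data would also be hard to read: the SAP provides for counting a second reduction, but its planned-dose denominator stays at 60 mg whatever was given.

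**Working it through.** The plan states no figure to reproduce here. The check compares the texts, followed by one arithmetic illustration.

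**Step 1. Count reductions along each route through Appendix E.** Take parts A, B and C once each.

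| Part | Phosphorus band | Reductions called for |
|---|---|---|
| A | 5.5–6.9 | 0 |
| A | ≥ 7 | 0 (same dose) |
| B | 5.5–6.5 | 0 |
| B | 6.6–6.9 | 0 |
| B | ≥ 7 | 1 |
| C | > 5.5–6.9, regimen not yet maximized | 0 |
| C | > 5.5–6.9, regimen maximized | 0 or 1 (to be considered) |
| C | ≥ 7 | 1 |

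Routes: 2 × 3 × 3 = 18. Reductions on a route = part B count + part C count. The total can exceed one only if part B was at 7 mg/dL or more and part C is one of its last two rows: 2 × 1 × 2 = 4 routes. Two of these (part C at 7 mg/dL or more) call for two reductions. The other two (part C on a maximized regimen) call for one and permit a second. The remaining 18 − 4 = 14 call for or permit at most one.

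These are routes, not subjects, and carry no weights. Subjects already reduced through a Table 5-1 event, or at an earlier pass through part C, can also meet the conflict and lie outside this count.

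**Step 2. Compare with the limit.** On the four routes, Section 5.3.1 gives permanent discontinuation if the second reduction is needed, while Appendix E gives continued treatment at a reduced dose.

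**Step 3. Find the dose level.** Appendix E names none. Table 5-1 gives 60 mg once daily, and SAP 10.3.1 uses 60 mg for every reduced period. The first reduction therefore has a defined level; nothing below 60 mg is defined.

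**Step 4. Effect on compliance.** SAP 10.3.1 defines compliance as cumulative dose ÷ planned cumulative dose × 100. SAP 7.4 excludes a subject from the per-protocol set below 75% over the period to the end of cycle 4 or treatment discontinuation. Suppose, for illustration only and not as a proposal, that a site did give a second reduction in whole 20 mg tablets, so 40 or 20 mg:

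- Within that period: 40/60 = 66.7%; 20/60 = 33.3%.
- Over 112 days, assuming 28 days at 80 mg, 28 at 60 mg, 56 at the lower level and no holds: planned = 28 × 80 + 84 × 60 = 7,280 mg.
- At 40 mg: actual = 2,240 + 1,680 + 2,240 = 6,160 mg, or 84.6%.
- At 20 mg: actual = 2,240 + 1,680 + 1,120 = 5,040 mg, or 69.2%.

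On these assumptions only the 20 mg case falls below 75%. The no-holds assumption is favourable: a held day adds nothing to the numerator, while the planned dose runs over the whole treatment duration.

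**The case against.** The strongest reply is that the documents already imply an order of precedence. Section 5.3.1 directs dose adjustment to Table 5-1 and cites the appendices as guidance on toxicity management. Appendix E describes itself as suggested guidelines, subject to clinical judgment and local standard of care. The discontinuation sentence is mandatory in form. On that reading Appendix E operates within the one-reduction limit, the absence of a level below 60 mg is what one would expect, and the SAP line simply follows Section 5.3.1 and exposes any breach.

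Much of this stands. It makes the conflict softer than one between two equal commands, and the SAP display rule means a second reduction would be visible. It does not close the gap. Table 5-1 itself delegates hyperphosphatemia to Appendix E, and no sentence says that the limit overrides part C.

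It is also true that a part C reduction can be a subject's first, since part A and the lower bands of part B leave the dose unchanged. A reader might infer that every part C reduction breaches Section 5.3.1; the 14 routes without conflict show otherwise. Nor must a later reduction mean a level below 60 mg, because a return to 80 mg is possible, although the text does not say how a reduction after that would count.

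Finally, enrolment has been halted and SAP 9.3 records that the study ended earlier than expected. That limits what a site-facing clarification can still change, but not the need for an exposure rule that matches what was done.

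**Conclusion.** The conflict is real and is confined to subjects already reduced who again meet an Appendix E reduction criterion. For them Section 5.3.1 and Appendix E lead to opposite outcomes when the further reduction is required, and may do so when it is only to be considered. How many subjects this concerns cannot be derived from the documents.

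Two stronger readings should be set aside. A reader might infer that the reduced dose is defined nowhere; Table 5-1 and SAP 10.3.1 both give 60 mg, and only a level below that is missing. A reader might also infer that the primary analysis is compromised. The ITT population depends on having received study drug, so its membership does not change, and sample size, power and alpha are unaffected.

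What can change is treatment continuation, treatment duration, the exposure and compliance summaries, and possibly per-protocol membership, which is supportive. The 84.6% and 69.2% figures rest on assumed doses, period lengths and no holds; they show that a per-protocol classification could turn on this, not that any did. Calling the SAP compliance figures wrong would presuppose that Appendix E prevails, which the documents do not say.

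**What to change.** Reconcile Protocol Section 5.3.1 with Appendix E parts B and C so that one statement governs a subject already reduced, for any reason, who again meets an Appendix E reduction criterion. The statement should also say how a reduction after a return to 80 mg counts. In the same edit, settle two neighbouring points: part B at 7 mg/dL or more both asks for a reduction to be considered and resumes with one, and part A resumes at the same dose while the Table 5-1 recovery row, read literally, gives 60 mg for the events listed above it. The choice of rule and dose belongs to the sponsor and its clinical advisers.

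Then align SAP 10.3.1: state what planned dose applies if a second reduction was given, and keep the category of more than one reduction consistent with that. If the protocol can no longer usefully be amended, record in the clinical study report which text was treated as governing, and list any subject with more than one reduction together with the doses taken.

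The cost is one protocol clarification and about one line in the SAP, to be settled before database lock. No new data are needed.
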